50 mg BID at the week 4 visit based on steady state concentration prior to investigational product (IP) administration ($C_{predose}$) result from week 2. Subjects who do not have a week 2 PK value in time for dose adjustment at the week 4 visit will be up-titrated at week 8 based on the steady state $C_{predose}$ result from week 2, if available. Subjects will be up-titrated at the week 4 or week 8 visits only if the week 2 $C_{predose}$ is < 200 ng/mL. Subjects with a week 2 $C_{predose} \geq 200$ ng/mL (or not available at week 8) will continue at 25 mg BID for the remaining of the study. Subjects randomized to placebo or to 25 mg BID will receive the assigned IP throughout the study. IP compliance will also be monitored. PK analysis and dose assignment will be blinded to the study team. To maintain blinding, all subjects will receive new IP supply at the week 4 and week 8 visits. The study includes transthoracic echocardiographic assessments (screening, week 8, and week 16). Enrollment of subjects with atrial fibrillation/flutter at the time of screening will be limited to approximately 20% of planned enrollment. Randomization will be stratified by presence or absence of atrial fibrillation/flutter via the interactive voice response system/interactive Web response system (IVRS/IWRS). An independent DMC will perform regular formal unblinded review of the accumulating study data. An independent CEC will adjudicate deaths, all hospitalizations, and selected nonfatal cardiovascular (CV) events (including possible MI or ischemia). The end of study (EOS) visit will be performed 4 weeks after the last dose of IP (Week 20 +3 days).

Vital signs, physical examinations, ECGs, Adverse Event/Serious Adverse Event assessments, clinical laboratory evaluations (see [Table 3](#)), and collection of concomitant medications will be performed at screening and at specified times per the Schedule of Assessments ([Table 2](#)). The overall study design is described in a [study schema](#) at the end of the protocol synopsis section.

The study endpoints are defined in [Section 10.1.1](#).

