- The subject experiences an asymptomatic decrease in systolic BP to < 80 mmHg (measured at 3 successive timepoints over approximately 15 minutes)
- The subject experiences symptoms associated with a HR > 120 bpm, systolic BP > 170 mm Hg, or diastolic BP > 110 mm Hg that are determined by the investigator to warrant termination of the dosing
- The subject experiences sustained systolic BP > 170 mm Hg (measured at 3 successive timepoints over approximately 15 minutes)
- The subject experiences a sustained diastolic BP > 110 mm Hg (measured at 3 successive timepoints over approximately 15 minutes)
- The subject experiences a sustained HR > 120 bpm (measured at 3 successive timepoints over approximately 15 minutes)
- The subject experiences a sustained (measured at 3 successive timepoints over at least 15 minutes) HR increase ≥ 25 bpm from screening or baseline AND HR > 100 bpm

If suspected adverse drug reactions or changes in vital signs, ECGs, or clinical laboratory results are observed during the study and, in the opinion of either the investigator or the Study Medical Monitor, these changes pose a significant health risk, dosing of an individual subject should be stopped and not resumed.

If administration of IP is stopped (up to 5 days after last IP) for any of the reasons above, a blood sample of 5 mL for PK analysis is to be collected as soon as possible .

If a subject experiences clinical signs or symptoms consistent with myocardial ischemia or infarction, the subject should receive immediate medical attention according to the

institution's usual standard of care. Serial cardiac troponin samples (troponin I or T) should be analyzed at the local laboratory. In addition, central laboratory analysis of serial samples for cardiac troponin I and/or creatine kinase MB fraction (CK-MB) as well as serial 12-lead ECGs should be collected. The investigator must notify Amgen immediately of any subject experiencing clinical signs or symptoms of myocardial ischemia or infarction.

The decision to rechallenge the subject should be discussed and agreed upon unanimously by the subject, investigator, and Amgen. If signs or symptoms recur with rechallenge, then omecamtiv mecarbil should be permanently discontinued.

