^a If early discontinuation, week 20 (EOS) assessments should be performed as close as possible to time of discontinuation

^b Serious adverse events are collected from signing the informed consent until 30 days after the last dose of IP or EOS, whichever is later, adverse events and PEPs from randomization until EOS, recording of PEPs and hospitalization only during visits to the study site (day 1, weeks 2, 4, 8, 12, 16, 20 [EOS]); if subject is not seen at the study site, AEs/SAEs/PEPs can be collected by phone

^c Predose in the morning, at study site

^d Performed as close as possible after the collection of PK sample at 2 hours \pm 30 minutes following IP administration.

^e If cardiac troponin is measured locally to evaluate suspected myocardial ischemia or infarction, send samples for troponin I/CK-MB, and PK (up to 5 days after last dose of IP) to the central laboratory

^f Serum pregnancy testing in females of childbearing potential, FSH/LH or estradiol at screening only, and only if applicable per exclusion criteria.

^g IP is taken twice daily except on the last day of administration (week 16 visit). Subjects randomized to 37.5 mg BID target dose and 50 mg BID target dose will initiate administration at 25 mg BID. Subjects will be up-titrated to 37.5 mg BID or 50 mg BID target dose at the week 4 visit based on steady state $C_{predose}$ result from week 2. Subjects who do not have a week 2 PK value in time for dose adjustment at the week 4 visit, will be up-titrated at week 8 based on steady state $C_{predose}$ result from week 2, if available. Subjects will be up-titrated at the week 4 or week 8 visits only if the week 2 $C_{predose}$ is < 200 ng/mL. Otherwise, they will continue at 25 mg BID.

^h Details of IP dispensation and reconciliation are described in the IPIM; dispensation and reconciliation timepoints may differ from the timepoints shown above; IP not dispensed at week 16 visit.

ⁱ Paper Diary will be dispensed at Day 1 and will be collected at week 16. Subjects will be instructed to enter each administration of IP from Day 1 to week 16 or early termination. The date and time of administration will be noted.

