Appendix A. Analytical Study Week Assignments

Selected endpoints will be summarized by scheduled study visits in descriptive analyses. Since the actual visits may not exactly coincide with their scheduled visit day, the actual visit day is mapped to the study visit by non-overlapping consecutive intervals covering the entire time continuum. The mapping intervals for all distinct schedules are summarized in the following table, for non-PK endpoints:

Scheduled visit	Actual Visit Day (Study Day)							
	VS*, CC, ECG	WT, CH, HE	PE	NT	ECHO	UR	DG	NYHA
BL/Day 1	≤ 1	≤ 1	≤ 1	≤ 1	≤ 1	≤ 1	≤ 1	≤ 1
Day 15 (Week 2)	> 1 – ≤ 21	> 1 – ≤ 35						> 1
Day 28 (Week 4)	> 21 – ≤ 42			> 1 – ≤ 42				
Day 56 (Week 8)	> 42 – ≤ 70	> 35 – ≤ 70		> 42 – ≤ 84	> 1 – ≤ 84	> 1 – ≤ 98		
Day 84 (Week 12)	> 70 – ≤ 98	> 70 – ≤ 98						
Day 112 (Week 16)	> 98 – ≤ 126	> 98 – ≤ 126		> 84	> 84			
Day 140 (Week 20)	> 126	> 126	> 1			> 98		

VS: vital signs; WT: body weight; CC: cardiac troponin and CK-MB; PE: physical examination; NT: NT-proBNP; ECHO: electrocardiography; CH: chemistry; HE: hematology; UR: urinalysis; DG: Digoxin.
*Vital signs on week 8 and 16 are to be measured multiple times for E-R analysis purpose, and the value before morning dose will be used for non-PKPD analysis.

Handling multiple records assigned to an analytical study day/week:

If there is more than one record in a study week interval, the analytical record for that specific study week will be defined as the record closest to the scheduled study day of that specific study week ($7 \times$ study week + 1). If two records are equidistant from the scheduled day, then the earlier record will be chosen. If there are multiple records on the same day, the last record will be used.

Exceptions to these rules are:

- vital signs, the latest one prior to first IP administration on that day will be used in the non-PKPD analysis;
- cardiac troponin, CK-MB, and creatine kinase, where the worst non-missing value within the interval will be used in the analysis.

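### SAP Appendix A assigns non-PK records to visits by study day alone, so an early stopper's EOS safety values are reported under Weeks 2 to 16 and can replace a scheduled on-drug visit

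*SAP*

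**What the plan says.** SAP Appendix A sets the visit for each record: "the actual visit day is mapped to the study visit by non-overlapping consecutive intervals covering the entire time continuum". Its scope is limited: "The mapping intervals for all distinct schedules are summarized in the following table, for non-PK endpoints". For vital signs, ECG and troponin/CK-MB the intervals end at days 21, 42, 70, 98 and 126. For weight, chemistry and hematology they end at days 35, 70, 98 and 126. The Week 20 row takes what lies beyond day 126, except that urinalysis enters it after day 98 and physical examination after day 1.

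If several records fall in one interval, the one used "will be defined as the record closest to the scheduled study day of that specific study week", with the target given as 7 x study week + 1 and ties going to the earlier record. For troponin, CK-MB and creatine kinase the worst value in the interval is used instead. The SAP has no rule for early-termination visits or for records taken after the last dose.

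The protocol describes EOS timing in two places. Section 3.1 says the EOS "visit will be performed 4 weeks after the last dose of IP (Week 20 +3 days", which fits a completer. Table 2 footnote a covers the other case: "If early discontinuation, week 20 (EOS) assessments should be performed as close as possible to time of discontinuation". Section 8.1 also lets a subject stop investigational product (IP) and remain in the study.

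SAP 10.8.2 to 10.8.4 then summarize laboratory values, vital signs and ECG by treatment group and scheduled assessment.

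**The concern.** Safety and tolerability is a primary objective, and change from baseline in laboratory values, vital signs and ECG is a named safety endpoint. A row labelled Week 8 is naturally read as the state of subjects at their Week 8 visit. Under Appendix A it may also hold a termination-visit value from a subject who has already stopped, with nothing to mark it. It may even hold that value in place of the visit the subject attended on drug.

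The withholding rules in protocol 6.2.1.2 and 6.3 are triggered by ischemia, blood pressure, heart rate and liver tests. Subjects who stop may therefore be selected on the very variables being averaged. The Week 20 row, in turn, lacks the end-of-participation values of subjects whose EOS came early.

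**Working it through.** **1. The intervals.** Each cut-off is the midpoint of adjacent scheduled days (15, 28, 56, 84, 112, 140), rounded down, using only the visits at which that assessment is done.
- Vital signs, ECG, troponin/CK-MB: (15+28)/2 = 21.5, so 21; then 42, 70, 98, 126.
- Weight, chemistry, hematology (no Week 4): (15+56)/2 = 35.5, so 35; then 70, 98, 126.
- Urinalysis: (56+140)/2 = 98.

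All agree with the SAP table. The cut-offs are interval arithmetic on planned visits and take no account of dosing status.

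**2. Where an early EOS record goes.** Possible early EOS days are 2 to 139, which is 138 days.

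| Assessment | EOS days placed before Week 20 | Count |
|---|---|---|
| Vital signs, ECG, troponin/CK-MB, weight, chemistry, hematology | 2 to 126 | 125 of 138 |
| Urinalysis (to Week 8) | 2 to 98 | 97 of 138 |
| Physical examination | none | 0 of 138 |

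These count days, not subjects, and say nothing about how often each day occurs. A completer is placed correctly: the earliest Week 16 visit is day 112 - 3 = 109, and 109 + 28 = 137, which is beyond 126.

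Example: EOS on day 30. Physical examination goes to Week 20, urinalysis to Week 8, vital signs, ECG and troponin to Week 4, and chemistry and hematology to Week 2. One visit lands in four rows. If a Week 2 chemistry sample exists on day 15 (distance 0 from target), the day-30 sample loses and appears in no by-visit row.

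**3. Replacement under the closest-record rule.** A scheduled visit on day v before target T is replaced by an EOS record on day e when v < e < 2T - v. For Week 8, with a visit window of days 53 to 59:

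| Visit day | EOS days that replace it, T = 57 (7 x 8 + 1) | T = 56 (table day) |
|---|---|---|
| 53 | 54 to 60 | 54 to 58 |
| 54 | 55 to 59 | 55 to 57 |
| 55 | 56 to 58 | 56 |
| 56 | 57 | none |
| 57 to 59 | none | none |

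Visit day 53 with EOS day 58: |53-57| = 4 against |58-57| = 1; with target 56, 3 against 2. Day 58 is used both times. Weeks 12 and 16 behave the same way. At Week 2 a day-12 visit is replaced by EOS on days 13 to 17. At Week 4 a day-28 visit is replaced only by EOS on day 29 (T = 29). For visits inside their window the gap is therefore at most 60 - 53 = 7 days.

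**4. Replacement under the worst-value rule.** For troponin, CK-MB and creatine kinase, a worse post-stop value anywhere in the interval (up to day 70 for Week 8) replaces the on-drug value. A better one does not.

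**5. Drug remaining.** Fraction = 0.5^(hours since last dose / half-life), with the mean half-lives of 17.1 to 23.2 h from the first-in-human intravenous study (protocol 2.2.2.1).
- 1 day: 0.5^(24/17.1) = 38%; 0.5^(24/23.2) = 49%.
- 2 days: 14% to 24%.
- 5 days: 0.5^(120/17.1) = 0.8%; 0.5^(120/23.2) = 2.8%; about 1-3%.

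**6. What is not touched.** SET and NT-proBNP are not measured at EOS. The maximum-QTc categories and the tables of the most extreme post-baseline value do not depend on visit mapping. PK is outside the mapping table.

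**The case against.** The SAP heads its rows by scheduled visit and never calls them on-treatment. Its safety approach runs to EOS whatever the last dose, as its treatment-emergent definition shows. Including values after stopping can be a legitimate choice, and the study is descriptive with no hypothesis test. Serious toxicity remains visible in the hepatic shift, QTc and worst-troponin tables. Closest-record replacement needs a visit before its target and an EOS within a week.

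All of that limits the point. It does not explain why one EOS visit should be spread over four rows, or why a termination record should displace a scheduled visit. The SAP does not state an intention to pool such values.

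Stronger readings are tempting but not supported:
- A reader might infer that these records are fully washed out and shrink the mean drug effect by a fixed share. That borrows the completer's four-week timing. Footnote a asks for EOS near discontinuation, when much of the drug may still be present. In the day-53/day-58 example with IP stopped on day 54, the record is only 4 days after the last dose.
- A reader might infer that Appendix A misplaces all records and that early stoppers are absent from Week 20. Physical examination always reaches that row, as do urinalysis after day 98 and any EOS after day 126, including that of a subject who stops IP but stays to day 140.
- A reader might conclude that every early EOS belongs in the Week 20 row. That would mix values taken near the last dose with the completers' four-week washout.

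**Conclusion.** The defect holds in a limited form. Applied as written, Appendix A reports an early stopper's EOS vital signs, ECG, weight, chemistry, hematology and troponin/CK-MB under Weeks 2 to 16 when EOS falls on or before day 126, and urinalysis under Week 8 when it falls on or before day 98. Such a record can replace a valid on-drug visit under the conditions shown. Scheduled visits attended after stopping IP are likewise not distinguished from on-drug visits.

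The consequence falls mainly on vital signs, ECG and the chemistry and cardiac markers named in SAP 10.8.2, which lists no hematology analyte for by-visit summary. The size and direction of any distortion depend on the time since last dose and on the stopping rate, and the documents do not give the latter. A pull toward baseline is possible but not established. The drug-remaining figures assume that intravenous half-lives in healthy volunteers carry over to the modified-release tablet in heart failure; slow release would leave more drug. The misplacement itself needs no such assumption: even with EOS four weeks after last dose, anyone stopping by day 98 has EOS by day 126 (98 + 28).

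This should be corrected in the SAP. It does not threaten the PK endpoints or SET.

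**What to change.** In SAP Appendix A:
1. Let a scheduled-visit record take precedence over an EOS or early-termination record in the same interval, applied before the closest-record and worst-value rules.
2. Identify EOS and early-termination records by visit label. Show those of early stoppers on a separate early-termination line, not merged with the completers' Week 20 row.
3. Flag records taken more than a stated interval after the last IP dose and show them on a separate off-treatment line in the by-visit safety tables. Five days would be one choice: 120/23.2 is about 5 half-lives. The protocol uses the same limit for PK samples after stopping (6.2.1.2), though not for judging safety values. If the sponsor prefers to keep such values in the visit rows, the SAP should say so.

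Item 3 alone would not catch the day-53/day-58 example with IP stopped on day 54, since that record is within five days of the last dose; items 1 and 2 do.

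The cost is a few sentences in Appendix A, a visit-label and last-dose condition in programming, and a slightly smaller n in some by-visit rows.

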^j Vital signs and PK samples at predose, at 2 hours \pm 30 minutes; 4 hours \pm 30 minutes; 6 hours \pm 30 minutes; 8 hours \pm 30 minutes after IP administration in the morning (0 h = start of IP); echocardiogram performed as close as possible after the collection of PK sample at 2 hours \pm 30 minutes following IP administration.

^k Vital signs and PK samples at predose and at 2 hours \pm 30 mins following IP administration. Echocardiogram should be performed as close as possible after the collection of PK sample at 2 hours \pm 30 minutes following IP administration.

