10.5.3 Secondary Endpoint

Echocardiographic parameter SET and its change from baseline at week 16 will be summarized by treatment group and scheduled assessment.

In addition, analysis will be performed to explore the potential relationship between omecamtiv mecarbil exposure and changes from baseline in SET. Differences between treatment groups in SET will be estimated via repeated-measures model, with difference estimates and their 95% CIs presented. The model will include the stratification factor,

treatment group, visit and the interaction of treatment group and visit. Subgroup analyses by baseline covariates in [Section 10.1.3](#) will be provided.

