10.8.3 Vital Signs

Vital signs, including HR (based on measurement of pulse), and their change from baseline will be summarized by actual treatment group and scheduled assessment.

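### Postdose blood pressure at weeks 8 and 16 has no planned safety summary, and postdose heart rate is covered only through the ECG taken after the 2 h PK sample

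*SAP*

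**What the plan says.** Protocol Table 2 (Section 7.1) asks at week 8 for "Vital signs and PK samples at predose, at 2 hours", and then at 4, 6 and 8 h. At week 16 it asks for "Vital signs and PK samples at predose and at 2 hours".

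SAP Appendix A gives the reason for the repeats: "Vital signs on week 8 and 16 are to be measured multiple times for E-R analysis purpose". The same footnote continues that "the value before morning dose will be used for non-PKPD analysis". The list of exceptions to the multiple-record rule repeats the choice: "vital signs, the latest one prior to first IP administration on that day will be used in the non-PKPD analysis".

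SAP Section 10.8.3 is the only section on the vital-sign safety analysis. It says "Vital signs, including HR (based on measurement of pulse), and their change from baseline will be summarized", by actual treatment group and scheduled assessment. It names no postdose time and no maximum or minimum.

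Protocol Section 10.5.4.3 calls for vital-sign summary statistics at every scheduled assessment and does not restrict them to predose. SAP Section 11, which records departures from the protocol's analyses, does not mention the restriction.

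**The concern.** Safety and tolerability form one of the two primary objectives, and change from baseline in vital signs is a named safety endpoint in both documents. Protocol Section 6.2.1.2 lists heart-rate increase and hypotension among the possible signs of ischemia with this drug, and several of its rules for withholding treatment are written in terms of blood pressure and heart rate.

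The protocol collects repeated readings across the dosing interval on two visit days. The SAP then sends only the predose reading to the safety tables. The remainder go to an analysis that is named but not described. If nothing more is written, the study could be reported without any tabulation by arm of blood pressure in the hours after a dose, although those data are the ones scheduled to show it.

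**Working it through.** No figure in the plan bears on this point, so there is none to reproduce. The check is a count of readings and a trace of where each one goes.

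**Count (protocol Table 2, week 8 and week 16 vital-sign footnotes)**
- Week 8: predose, 2, 4, 6, 8 h = 5 readings, 4 postdose.
- Week 16: predose, 2 h = 2 readings, 1 postdose.
- Total 5 + 2 = 7; predose 2; postdose 4 + 1 = 5; 5/7 = 71%.
- Trial maximum: 80 × 5 = 400 postdose readings, of which 20 × 5 = 100 are on placebo and 60 × 5 = 300 on active drug. This assumes that every subject attends both visits and has every reading.

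**Where each reading goes**

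| Measurement, weeks 8 and 16 | Planned safety summary | Other stated use |
|---|---|---|
| Predose BP and pulse | SAP 10.8.3 | none needed |
| BP at 2 h (both visits) and at 4, 6, 8 h (week 8) | none | exposure-response, not specified |
| Heart rate at about 2 h | RR from the ECG, SAP 10.8.4 | pulse reading: exposure-response, not specified |
| Heart rate at 4, 6, 8 h (week 8) | none | exposure-response, not specified |

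**Is there an exposure-response plan for vital signs?** Protocol Section 10.5.3 describes one for "omecamtiv mecarbil exposure and changes from baseline in SET", and the synopsis likewise refers only to SET. SAP Section 13 places that SET analysis outside the SAP. Neither document describes such an analysis of blood pressure or heart rate.

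**How far does the ECG substitute?** Table 2 times the week 8 and week 16 ECGs just after the 2 h PK sample. SAP Section 10.8.4 summarizes RR and its change from baseline by visit, so heart rate at about 2 h is reported indirectly. The same section excludes observations showing an artificial pacemaker, atrial fibrillation, atrial flutter or bundle branch block. Enrollment with atrial fibrillation or flutter may reach about 20% of 80, that is 0.20 × 80 = 16 subjects. The documents give no expected number for the other exclusions. Blood pressure has no substitute.

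**How does the SAP treat comparable measures?** Section 10.8.4 categorizes QTc by each subject's maximum change and counts unscheduled readings. Appendix A takes the worst value in the window for troponin, CK-MB and creatine kinase. Vital signs get no extreme-value summary.

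**Do concentrations differ over the interval?** Protocol Table 1 (simulated, Japanese), taking AUC over 12 h, gives Cmax divided by average concentration:
- 25 mg: 277/(2759/12) = 277/229.9 = 1.20
- 37.5 mg: 461/(4613/12) = 461/384.4 = 1.20
- 50 mg: 614/(6143/12) = 614/511.9 = 1.20

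The half-life of 17.1 to 23.2 h (intravenous, healthy volunteers, protocol Section 2.2.2.1) implies a fall over 12 h of 2^(12/17.1) = 1.63-fold to 2^(12/23.2) = 1.43-fold under simple exponential decline. So predose and postdose readings are probably taken at different concentrations. These ratios are for scale only. Neither document gives a time to peak for the modified-release tablet.

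**The case against.** The predose choice has a sound reason. Day 1 vital signs are also predose, so change from baseline compares like with like, and one value per visit is a normal convention in a descriptive study. That stands, and the fix keeps it.

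A reader might infer that postdose heart rate and blood pressure are never reported. The documents do not support this. RR at about 2 h is in a planned table. The exploratory heart-rate endpoint may come from the same ECG: SAP Section 10.7 does not name its source, but Section 10.4 lists baseline ECG heart rate beside the echocardiographic parameters that Section 10.7 models. The readings also have a stated exposure-response use. The SAP covers only the analyses run by the biostatistics department and leaves PK analysis to another group, so a plan may exist elsewhere. What can be said is that neither of these documents contains one.

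A reader might also infer that tolerability is judged only at trough. That goes too far. Vital signs at weeks 2, 4 and 12 are not tied to predose and may be taken at any time in the visit. Adverse events, the withholding rules and roughly monthly unblinded data monitoring also apply throughout treatment.

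Finally, a scheduled assessment in protocol Section 10.5.4.3 could be read as a visit. On that reading the SAP chooses within the protocol rather than narrowing it. The gap in the output would be the same.

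**Conclusion.** The point holds in a limited form. In the safety analysis, vital signs at weeks 8 and 16 are represented by the predose value alone. Postdose blood pressure has no specified summary in either document. Postdose heart rate is covered only at about 2 h, through RR, and only for observations that survive the rhythm and conduction exclusions. The size is five of seven scheduled readings per subject at these two visits, on the assumption of full attendance.

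No statement about the size of a missed effect is justified. A reader might infer from Table 1 that predose readings understate a peak effect by about one third: a symmetric profile puts trough at 2 × 229.9 − 277 = 183, and 1 − 183/277 = 0.34. That needs an assumed profile shape and an effect strictly proportional to concentration with no delay, and neither document supports these for blood pressure or heart rate. The dog studies in protocol Section 2.2.1 report no increase in heart rate and no noticeable effect on blood pressure.

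This is a reporting gap that is cheap to close. It is not a flaw in design or data collection, and sample size is unaffected.

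**What to change.** Keep predose as the by-visit value. In SAP Section 10.8.3 and Appendix A, add:

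1. Descriptive summaries of systolic pressure, diastolic pressure and pulse heart rate at each nominal time at weeks 8 and 16, as change from baseline and as change from the same day's predose reading.
2. Each subject's largest postdose increase and largest postdose decrease in each measure. Report the two visits separately, because week 8 has four postdose readings and week 16 has one.

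Show both by treatment group including placebo. Record the predose rule in SAP Section 11, and cite the document that will hold the exposure-response analysis of vital signs, if there is one.

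The cost is SAP wording and two further descriptive tables from data already scheduled for collection. Extremes taken over repeated readings are inflated by chance, so they must be read against placebo, which also carries any time-of-day effect.

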7. STUDY PROCEDURES

7.1 Schedule of Assessments

Table 2. Schedule of Assessments

Timepoint - Day/Week/Month (window)*	Screen	D1	D7	W2 D15 (-3)	W4 D28 (+3)	D34 (+3)	W8 D56 (±3)	D62 (+3)	W12 D84 (±3)	W16 D112 (±3)	W20 ^a D140(+3) EOS
General Procedures											
Informed consent	X										
Medical history and demographics	X										
Vital Signs (HR, BP)	X	X ^c		X	X		X ^j		X	X ^k	X
AEs/SAEs/PEPs ^b	X	X		X	X		X		X	X	X
AEs/SAEs and IP compliance verification by phone or other contact			X			X		X			
Concomitant therapy	X	X		X	X		X		X	X	X
Physical examination	X										X
Body height		X									
Body weight		X		X			X		X	X	X
ECG	X	X ^c		X	X		X ^d		X	X ^d	X
Echocardiogram	X						X ^j			X ^k	
Central Laboratory											
PK samples ^e		X ^c		X ^c	X ^c		X ^j		X ^c	X ^k	
Chemistry (including eGFR at screening)	X			X			X		X	X	X
Hematology	X			X			X		X	X	X
Urinalysis		X					X				X
Troponin I, CK-MB ^e		X ^c		X	X		X		X	X	X
NT-proBNP		X ^c			X		X			X	
Samples for Development Therapeutic Monitoring Assay					X				X		
Serum pregnancy, FSH/LH or estradiol ^f	X										X
Digoxin sample (in subjects receiving digoxin)		X		X							
Investigational Product^g											
IP dispensation and/or administration at site		X		X	X		X		X	X ^h	
IP diary dispensation or collection ⁱ		X								X	
IP reconciliation (tablet count)				X	X		X		X	X	

Footnotes displayed on the next page of the Table

AE = adverse event; BP = blood pressure; CK-MB = creatine kinase-MB; ECG = electrocardiogram; eGFR = estimated glomerular filtration rate; EOS = end of study; HR = heart rate; IP = investigational product; NT-proBNP = N-terminal pro-B-type natriuretic peptide; NYHA = New York Heart Association; PEP = potential endpoint; PK = pharmacokinetic; SAE = serious adverse event.

Please note: vital signs, ECGs, and laboratory samples can be collected at any time during the study visit, unless otherwise specified below.

Visit Windows: For week 2 visit, the visit date could be 3 days prior to the scheduled date of W2; for week 4 visit, the visit date could be 3 days after the scheduled date of W4; for weeks 8, 12, and 16, the visit dates could be 3 days prior to or after the scheduled date of W8, W12, and W16, respectively; for week 20 visit (EOS), the visit date could be up to 3 days after the scheduled date of W20. The Day 34 and 62 telephone calls could be 3 days after the scheduled date of contact.

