7.2.4 Vital Signs

The following measurements must be performed: systolic/diastolic BP and HR. Subjects should be in a seated or semi-recumbent position for at least 5 minutes before taking vital sign measurements. The position selected for a subject should be the same that is used throughout the study and documented on the vital sign eCRF. Any abnormal measurements may be repeated and reported on the eCRF. All values must be verifiable on the source documents.

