4.1.3 Safety Endpoints

Safety endpoints are as follows:

- Subject incidence of adverse events (AEs)
- Changes from baseline in laboratory values and vital signs
- Changes from baseline in ECG

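### A repeated abnormal pre-dose blood pressure or heart rate reading reaches no planned vital-sign table, because SAP Appendix A keeps only the latest pre-dose record and SAP 10.8.3 has no extreme-value summary (minor)

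*SAP*

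**What the plan says.** Protocol 7.2.4 states: "Any abnormal measurements may be repeated and reported on the eCRF". Repeating is optional, no definition of abnormal is given, and nothing says that the repeat overwrites the first reading.

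SAP Appendix A decides which record is analysed when a day holds several. Its general rule is "If there are multiple records on the same day, the last record will be used". A list of exceptions follows, and the first is for vital signs: "vital signs, the latest one prior to first IP administration on that day will be used in the non-PKPD analysis". The table footnote says the same for weeks 8 and 16, when serial readings are taken: "the value before morning dose will be used for non-PKPD analysis". The second exception works differently: "cardiac troponin, CK-MB, and creatine kinase, where the worst non-missing value within the interval will be used in the analysis". Under SAP 6.2 the baseline vital sign is the last non-missing value up to Study Day 1.

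The safety endpoint in SAP 4.1.3 is "Changes from baseline in laboratory values and vital signs". The planned analysis in SAP 10.8.3 is: "Vital signs, including HR (based on measurement of pulse), and their change from baseline will be summarized by actual treatment group and scheduled assessment". Protocol 10.5.4.3 likewise plans summary statistics at each scheduled assessment and nothing more.

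**The concern.** The protocol mentions repeats only for abnormal readings, so replacement works in one direction. A normal first reading is kept. An abnormal one, if repeated before dosing, gives way to a value that tends to lie nearer the subject's own mean. With no worst-value, threshold or maximum-change table for vital signs, the first reading then appears in no vital-sign output.

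The SAP handles comparable safety data differently. QTc is categorised by maximum value and maximum change with unscheduled assessments included (SAP 10.8.4), and troponin, CK-MB and creatine kinase take the worst value in the interval. Yet blood pressure and heart rate are the variables with numeric limits for withholding study drug in Protocol 6.2.1.2, and safety is part of the primary objective. With about 20 subjects per arm, one subject is 1/20 = 5% of an arm, so losing one or two extreme readings can remove a visible imbalance.

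**Working it through.** The documents give no figure for this rule, so there is none to reproduce. The check has two parts.

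**1. Which record is selected.** Both rules applied to six same-day patterns:

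| Pattern | General rule | Vital-signs exception |
|---|---|---|
| A. Weeks 2, 4, 12: abnormal pre-dose, repeat pre-dose | repeat | repeat |
| B. Weeks 2, 4, 12: abnormal pre-dose, repeat post-dose | repeat | abnormal reading |
| C. Weeks 2, 4, 12: both post-dose | repeat | no qualifying record |
| D. Week 8: normal pre-dose, abnormal at 2 h and repeated, then 4, 6, 8 h | 8 h value | pre-dose value |
| E. Week 8: abnormal pre-dose, repeat pre-dose, then serial readings | 8 h value | repeat |
| F. Week 20 | repeat | no qualifying record |

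The two rules agree only in A. Under the exception, which governs, the abnormal reading is replaced in A and E. It survives in B. In D the 2 h reading is left out because it is post-dose, not because it was repeated.

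C and F have no answer under the exception. Dosing ends at week 16 (Protocol 6.2.1.1), so week 20 has no dose that day. At weeks 2, 4 and 12 no pre-dose timing is set for vital signs, and Protocol 7.1 says "vital signs, ECGs, and laboratory samples can be collected at any time during the study visit, unless otherwise specified below". The only text left for these visits is the general last-record rule.

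**2. Size, on assumed values.** The documents give no blood pressure SDs. Assume mean systolic pressure 112 or 117 mm Hg, between-subject SD 14 and within-visit SD 5, 8 or 10. Each reading is the subject's mean plus within-visit error. Every first reading below 90 is repeated once, pre-dose. The cut-off of 90 is borrowed from exclusion criterion 209 for illustration; it is not a withholding limit.

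*Tails.* Let p be the share of first readings below 90 and r the share of those whose repeat is 90 or above. Then the analysed share below 90 is p × (1 − r).

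- Eligibility ignored: p = 3.4% to 10.0% and r = 0.36 to 0.63. At mean 112, SD 10: 10.0% × (1 − 0.56) = 4.4%. Over all settings the analysed share is 2.0% to 4.4%.
- Screening reading required to be 90 to 160 (criterion 209): p = 1.5% to 6.3% and r = 0.62 to 0.74. At mean 112, SD 10: 6.3% × (1 − 0.70) = 1.9%. At mean 117, SD 5: 1.5% × (1 − 0.65) = 0.5%.

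*Means.* The shift in a visit mean is p × (average rise on repeat). Ignoring eligibility, at mean 112, SD 10, that is 10.0% × 10.3 = 1.03 mm Hg, the largest value; the smallest is 0.13. The endpoint is change from baseline, and under the same rule baseline shifts too:

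- No drug effect: the two shifts cancel, so the bias is about 0.
- True fall of 5 mm Hg, eligibility applied, mean 112, SD 10: the shift is 1.26 on treatment and 0.82 at baseline. The estimated fall is 5 − (1.26 − 0.82) = 4.56. Over all settings it is 4.6 to 4.9.

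**The case against.** A reader might infer that the SAP analyses the last record of the day for vital signs. It does not: on dosing days the exception directly below that sentence replaces it, and replacement then needs a repeat taken before the dose.

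A reader might also infer that abnormal readings disappear from the safety evaluation. The documents do not support that. Repeats are reported on the eCRF with no instruction to overwrite. A clinically relevant change can be reported as an adverse event, and SAP 10.8.1 tabulates adverse events and those leading to withdrawal of study drug. The DMC reviews unblinded data about monthly.

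The strongest argument against acting is that no planned output is materially wrong. Part 2 gives near-zero bias in mean change without a drug effect and slight attenuation with one, in a descriptive study. The counts it shows falling are counts the plan never promised. A sustained drug effect would largely persist on repeat, and the numeric withholding rules in Protocol 6.2.1.2 mostly ask for confirmation at three successive timepoints, so a single reading carries limited weight.

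Most of this stands, and it is why the point is minor. It leaves two gaps. No vital-sign table shows extremes, though the SAP gives QTc and cardiac markers that treatment. And the record rule is silent at week 20 and for visits with post-dose readings only.

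**Conclusion.** The concern holds in a limited form. An abnormal pre-dose reading repeated before dosing is replaced in the analysis, baseline likewise takes the last value, and neither the replaced reading nor the post-dose readings at weeks 8 and 16 appear in a planned vital-sign safety table.

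The inference that by-visit means are pushed materially toward normal is not supported: the effect on mean change is about 0 to 0.4 mm Hg (5 − 4.6) in the settings tried. The loss is in the tails. Low systolic counts would fall by 36% to 63% ignoring eligibility, and by 62% to 74% with it applied and no drug effect. Both ranges rest on assumed means and SDs and on every low reading being repeated pre-dose. Since repeating is optional, they are upper-end figures. Severity: minor.

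**What to change.** **SAP 10.8.3.** Add the number and percentage of subjects by arm with any post-baseline reading (scheduled, repeat, unscheduled or post-dose) beyond the numeric blood pressure and heart rate limits already written in Protocol 6.2.1.2. Use those limits unchanged, and footnote that a single reading beyond a limit does not mean that a withholding rule was met.

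**SAP Appendix A.** State which record is used where no pre-dose reading exists: week 20, and post-dose-only readings at weeks 2, 4 and 12.

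Averaging all readings in the same pre-dose slot, at baseline as well, is optional. It is a matter of convention and would change the means little.

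**Cost.** SAP wording and one descriptive table, with no new data collection provided that the eCRF keeps both the first reading and its repeat; confirm this before lock. The downside is that the table will include single unconfirmed readings.
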